1 ADDITIONAL INFORMATION

1.1 Sample Code for Adjusted Communication Success Rate

The following is sample code that will provide adjusted estimate of the communication success and 97.5% one-sided lower pointwise confidence limit:

where 'success' is an indicator of success for each communication test in all postures, 'subject' is the subject ID for all subjects that are evaluable for the endpoint, 'comm_success' is the adjusted communication success rate and 'lower_CL' is the 97.5% one-sided lower pointwise confidence limit.

1.2 Additional Information Regarding Secondary Effectiveness Endpoint

For a full description of this endpoint please refer to Section 11.1.5 of the MODULAR ATP Clinical Study Protocol.

Data used for the analysis of the Secondary Effectiveness Endpoint will be provided to the statistician performing the analysis as a validated dataset provided by the Boston Scientific engineering team with the normalized sensor-indicated rate and the normalized workload during the treadmill test.

The model for this endpoint is outlined in Section 11.1.5.3 of the MODULAR ATP Clinical Study Protocol. Subject-specific slopes from each test will be calculated by performing a general linear model with normalized sensor rate as the outcome and normalized workload as the predictor. For the purposes of evaluating the endpoint a zero-intercept model will be fit.

1.3 Ancillary Objectives

Additional information regarding the ancillary objectives outlined in Section 11.2 of the MODULAR ATP Clinical Study Protocol is found below:

- Summary of the mCRM Therapy System implant procedure characteristics:
 - Initial implant success rate of the EMPOWER PG Number of implants out of all attempted implants
 - Initial implant success rate of the S-ICD (De Novo Implants) Number of implants out of all attempted implants
 - Procedure Times (both EMPOWER PG and S-ICD)
 - Fluoro Time (both EMPOWER PG and S-ICD)
 - Implant position (both EMPOWER PG and S-ICD)
 - o Number of EMPOWER PG repositions performed at implant
 - Summary of use of anticoagulation
 - Summary of use of antibiotics
 - o Summary of use of antiplatelets
- Summary of pacing impedance and sensing amplitude at protocol-required follow ups
- Summary of ventricular tachycardia (VT)/ ventricular fibrillation (VF) S-ICD conversion and sensing interaction testing (Implant or Pre-Discharge)
 - Time to shock for induced episodes
 - o Detected rhythm
 - \circ Final Conversion Success Rate successful conversion at \leq 65J shock
 - Summary of Communication Threshold Test at Implant, Pre-Discharge, 1-Month Visit and available Semi-Annual visits
 - Summary of Communication Test results at available Semi-Annual visits
 - Summary of incidence and threshold for Communication Muscle Stimulation at Implant
 - Summary of number of postures with a successful communication test at the 6 Month Visit
 - Summary of EMPOWER PG PCT at protocol-required follow ups
 - Summary of spontaneous treated VT/ VF episodes
 - o Initial Rhythm
 - Method of treatment (ATP, Shock, both)
 - $\circ \quad \mbox{Final Conversion Success} \mbox{Any method}$
 - Time to first therapy (ATP or shock)
 - Summary of communication outcome between the S-ICD and EMPOWER MPS during treated spontaneous episodes, where

communication success will be reported as the number of qualified episodes with ATP delivered over the number of qualified episodes where ATP was requested

- Incidence of syncope related to treated and untreated spontaneous episodes of VT/ VF above the lowest programmed rate cutoff
- Incidence and appropriateness of post-shock demand pacing by the EMPOWER PG
- Summary of Inappropriate Therapy
 - Type of therapy delivered
 - Initial Rhythm
 - Arrythmia acceleration due to ATP delivery
 - Arrythmia induction due to ATP delivery
- Summary of Major EMPOWER MPS System- and Procedure-related Complications through both 6 and 12 months after the implant procedure
- Summary of mCRM Therapy System-related complications through both 6 and 12 months after the implant procedure*
- Summary of the EMPOWER PG performance from Holter Monitor recording
- Summary of EMPOWER PG battery charge remaining to End of Service (EOS) at protocol-required follow ups
- Summary of S-ICD PG remaining battery to Elective Replacement Indicator (ERI) per protocol-required follow ups (baseline adjusted to time of enrollment for S-ICD PGs implanted prior to enrollment in MODULAR ATP)

*S-ICD PG replacement due to normal battery depletion will not be included in this analysis

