#### 6.6 Study Rationale

Patients may benefit from ventricular arrhythmia termination with ATP because it can avoid a shock that is often painful and consumes battery energy. The effectiveness of ATP therapy in terminating VT is well established and recognized by international guideline recommendations for ICD programming. Therefore, ATP therapy effectiveness is not the primary focus of the study. Instead, the MODULAR ATP Clinical Study will focus on the novel aspects of the mCRM Coordinated System for the delivery of ATP.

The MODULAR ATP Clinical Study evaluates the safety and effectiveness of the EMPOWER MPS and the unique aspect of the mCRM Coordinated System, which is the unidirectional transmission of conductive communication signals from the S-ICD System to the EMPOWER PG. The EMPOWER PG is designed to recognize communication signals sent from the S-ICD coil towards the S-ICD PG, creating a communicating vector. Because this communication can be affected by the orientation of the devices relative to each other, the primary effectiveness endpoint will demonstrate communication success in varied orientations by altering body postures of subjects. Communication is tested by commanding a communication signal from the S-ICD that results in EMPOWER pacing for 10 beats above the subject's intrinsic rate.

Additionally, communication success will be demonstrated during spontaneous ventricular tachyarrhythmia episodes.

The effectiveness of the EMPOWER PG will be assessed by measuring adequate Pacing Capture Threshold (PCT) during follow-up visits post-implant. PCT has been shown to be affected by multiple factors, including the method and stability of fixation. The EMPOWER PG is designed to deploy using 4 active-fixation nitinol talons, as compared to the conventional active-fixation screw or passive-fixation tine engagement used in a transvenous lead system. The MICRA leadless pacemaker uses a similar mechanism consisting of 4 active-fixation nitinol tines, but the NANOSTIM leadless pacemaker uses a different mechanism consisting of an active-fixation fixed screw. Results from other

<sup>15 Wathen M. Implantable cardioverter defibrillator shock reduction using new antitachycardia pacing therapies. *Am Heart J.* 2007 Apr;153(4 Suppl):44-52.

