#### Table 10-8: EMPOWER PG Programming

#### 10.4.4.2 S-ICD Programming

Therapy zone and ATP settings are recommended to be programmed per **Table 10-9** for primary prevention subjects and **Table 10-10** for secondary prevention subjects. All other programming parameters (e.g., sensing vector, gain) are left to the discretion of the investigator. Rationale for not following the recommended programming parameters will be collected.

S-ICD Programming for Primary Prevention Subjects (all Recommended programming, except where noted)				
Therapy Zone	Rate	ATP Parameters		
Conditional Shock Zone	180-230 bpm 	At least 1 ATP request Required ; up to 3 acceptable (ATP scheme is per physician discretion)		
Shock Zone	>230 bpm	Quick Convert ATP ON		

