## 21.2 Clinical Events Committee

A Clinical Events Committee (CEC) is an independent group of individuals with pertinent expertise that reviews and adjudicates all treated spontaneous episodes with available source documentation, relevant AEs, and all subject deaths reported by study investigators. Relevant AEs are those deemed to be attributed to either/ both of the PGs in the mCRM Coordinated System, the S-ICD electrode, or the procedure to implant the EMPOWER PG. The CEC will review a safety event dossier for each submitted AE or death, which may include copies of subject source documents provided by study sites, BSC reserves the right to submit other AEs as well, if deemed necessary.

Committee membership will include practitioners of cardiology, as well as other experts with the necessary therapeutic and subject matter expertise to adjudicate the event categories outlined above. CEC responsibilities, qualifications, membership, and committee procedures are outlined in the CEC charter.

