Permanent Loss of Device Function	Refers to: 1) the permanent loss of shock therapy and/or post shock pacing (S-ICD only); 2) permanent loss of appropriate sensing in all available sensing configurations (oversensing that results in persistent inappropriate shocks or undersensing that could lead to undetected arrhythmias) (S-ICD only). Loss of device function includes programming the PG permanently off or temporarily off in advance of an explant/revision (applies to both EMPOWER and S-ICD.
Patient/ Potential Subject	A person who is a potential candidate for the MODULAR ATP Clinical Study
Subject	A person who has been enrolled into the MODULAR ATP Clinical Study
Spontaneous episode	Any arrhythmia that is stored by the S-ICD pulse generator. For the purpose of the MODULAR ATP Clinical Study, only ventricular arrhythmias will be collected.
Time 0	Timing of study-required follow ups will be determined based on the date that the mCRM Coordinated System is implanted (successful implant of both the S-ICD System, with clinical firmware, and EMPOWER PG)
	Note: Subjects classified as a Partial Implant that are implanted with an EMPOWER PG must be followed according to this protocol, with all relevant EMPOWER PG device data and testing collected. Time 0 for the purpose of determining timing of follow ups for these subjects is the day it is determined the S-ICD will not be implanted.
Time to therapy for inductions	Time to therapy for induced episodes is defined as the interval starting 2000ms after the last induction artifact (the time of the post induction refractory) and ending at the onset of the shock deflection on the S-ECG recording.
Time to therapy for spontaneous episodes	Time to therapy for spontaneous episodes is defined as the interval starting when the cycle length of the patient's rhythm is greater or equal to the lowest programmed zone cutoff and measured until the start of delivery of ATP pulses or the shock marker.

Page 124 of	148
	_
C - NAP O WE SHO	
102931 10102931	
O DE LA LASSE AND	

MODULAR ATP	
	Page 125 of 148

MODULAR ATP	
	Page 126 of 148
	C I
	_
	I

MODULAR ATP
Page 127 of 148

MODULAR ATP	
	Page 129 of 148
	6

MODULAR ATP	
	Page 130 of 148

Page 131 of 148

Page 134 of 148

MODULAR ATP

MODULAR ATP Page 136 of 148

Page 137 of 148

MODULAR ATP

MODULAR ATP	
	Page 138 of 148

MODULAR ATP	
	Page 142 of 148

Page 144 of 148

MODULAR ATP

Page 148 of 148

MODULAR ATP

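### The spontaneous-episode communication rate in SAP 1.3 may drop unanswered ATP requests that end without a shock, and its per-episode scoring hides a failed first request

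*SAP*

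**What the plan says.** Protocol Section 6.6 presents S-ICD-to-EMPOWER communication as what is new in the system. Beyond the posture tests, it says that "communication success will be demonstrated during spontaneous ventricular tachyarrhythmia episodes". The only analysis I find for that statement is in SAP 1.3, under the summary of treated VT/VF episodes: a "Summary of communication outcome between the S-ICD and EMPOWER MPS during treated spontaneous episodes". There, "communication success will be reported as the number of qualified episodes with ATP delivered over the number of qualified episodes where ATP was requested".

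The same SAP list gives "Method of treatment (ATP, Shock, both" as the treatment categories. Protocol Section 25.2 defines time to therapy for a spontaneous episode as "measured until the start of delivery of ATP pulses or the shock marker". Neither document defines *treated* or *qualified* in its readable text.

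On the number of requests, Tables 10-9 and 10-10 in Protocol Section 10.4.4.2 require at least one ATP request in the conditional shock zone, with "up to 3 acceptable (ATP scheme is per physician discretion". On review, Protocol Section 21.2 says that the CEC "reviews and adjudicates all treated spontaneous episodes with available source documentation"; it gives no such role for untreated episodes.

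**The concern.** A communication success rate should have in its denominator every episode in which communication was attempted. Here entry may depend on the result. Delivered ATP makes an episode treated, so every success enters. An unanswered request may enter only if a shock follows. If the arrhythmia stops by itself first, nothing was delivered and the failure may never be counted.

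The second issue does not depend on what *treated* means. One delivered ATP makes the whole episode a success, even if an earlier request in it went unanswered.

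What is at stake is the estimate of communication in actual ventricular arrhythmia. The four-posture tests pace slightly faster than the intrinsic rhythm (Protocol Section 10.3.4.1), and conversion testing uses asynchronous pacing and a shock (Section 10.3.4.7). Neither measures whether an ATP request is answered during VT.

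**Working it through.** **No figure to reproduce.** The documents give no expected rate, episode count or sample size for this summary.

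**Step 1: which episodes can drop out, if *treated* means therapy delivered.**

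| Episode with an ATP request | Therapy delivered | In denominator | Scored |
|---|---|---|---|
| Request answered | ATP, or ATP and shock | Yes | Success |
| Request unanswered, shock follows | Shock | Yes | Failure |
| Request unanswered, no shock | None | No | Not counted |

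Only failures can be lost, so the bias is zero or upward.

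**Step 2: possible size.** Let s be the true share of episodes with a request in which ATP is delivered, and f the share of failed-communication episodes that end without therapy. Both are assumptions.

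Reported rate = s / [s + (1 − s)(1 − f)]

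- s = 88%, f = 20%: 0.88 / (0.88 + 0.12 × 0.80) = 0.88 / 0.976 = 90.2%
- s = 88%, f = 50%: 0.88 / (0.88 + 0.12 × 0.50) = 0.88 / 0.940 = 93.6%

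| True rate s | f = 0 | f = 10% | f = 20% | f = 50% |
|---|---|---|---|---|
| 80% | 80.0% | 81.6% | 83.3% | 88.9% |
| 88% | 88.0% | 89.1% | 90.2% | 93.6% |
| 95% | 95.0% | 95.5% | 96.0% | 97.4% |

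For f from 10% to 50%, the bias runs from +0.5 points (s = 95%, f = 10%) to +8.9 points (s = 80%, f = 50%). At s = 88% it is +1.1 to +5.6 points.

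**Step 3: the other reading.** If the S-ICD files every episode with an ATP request as treated, the third row of the first table enters as a failure and the reported rate equals s. But that episode then fits none of the three treatment categories and has no time to first therapy, so the SAP needs a rule for it under this reading too.

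**Step 4: per-episode scoring.** Assume that each request succeeds with probability 70% and that up to three are made while the VT persists.

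- Independent requests: 1 − (1 − 0.70)³ = 1 − 0.027 = 97.3% of episodes score as successes.
- Requests that all succeed or all fail together: 70%.

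The per-episode figure can therefore lie anywhere from the single-request rate to well above it. In clinic the protocol is stricter: when a test is repeated in a posture at the 6 Month Visit, only the first at the initial programmed setting counts for the endpoint (Section 10.7.3.2).

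**The case against.** The strongest reply is that the selection mechanism may not exist. The link is one-way (Protocol Section 6.6), and treated and untreated are also names of S-ICD programmer reports. A device that receives no acknowledgement might well label an episode by its own action, the request, and not by EMPOWER's response. Unanswered requests would then stay in the denominator. This stands: the documents do not say how such an episode is filed, and the time-to-therapy wording does not define *treated*. A definition may also sit in the CEC charter or in the appendix pages that cannot be read here; their absence is not a fault in the plan.

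It could also be argued that the bias might run downward, if only shocks made an episode treated and ATP-only successes were lost. That does not fit the SAP, which lists ATP alone as a treatment method.

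The inputs are open to challenge as well. A history of non-sustained MVT is one of several inclusion routes (Section 8.2), but it does not show how often VT lasts long enough to trigger an ATP request and then stops before a shock. Section 6.6 says that communication depends on device orientation, so requests within one episode are probably correlated and 97.3% is an upper illustration. Both points stand.

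Finally, per-episode scoring is stated openly and is a legitimate measure. That is true, but alone it does not show how often the first request is answered.

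**Conclusion.** The point holds in conditional form. Under the reading that the nearest wording favours, the rate can only be right or too high; under the other plausible reading the selection bias is zero. The 90.2% to 93.6% range rests on an assumed true rate of 88% and an assumed 20% to 50% of failed-communication episodes ending without therapy. The documents supply neither input for this summary. Per-episode scoring is a separate limitation that applies under both readings.

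A reader might infer two stronger conclusions:

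- **That upward bias is established.** It is not, because *treated* and *qualified* are undefined in the readable text.
- **That the study's communication claim against 88% is inflated.** The documents do not support this. The 88% goal belongs to Primary Effectiveness Endpoint 1, which uses the four-posture tests at 6 months (Protocol Section 11.1.4). The spontaneous-episode rate has no hypothesis, goal or alpha, and study success rests on Safety Endpoint 1 and the primary effectiveness endpoints (Section 11.5.1). The value of 88% is used above only as an illustrative true rate.

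The change is still worth making, because the proposed denominator is right whichever way the device files these episodes.

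**What to change.** In SAP 1.3:

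1. Set the denominator to all spontaneous VT/VF episodes, treated or untreated, in which the S-ICD issued at least one ATP request, and define *qualified* in those terms.
2. Report the proportion of episodes whose first request was answered, beside the proportion in which any request was answered.
3. State how an episode with only unanswered requests and no shock is classified in the treatment-method and time-to-therapy summaries.

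The data should largely be in hand: Protocol Sections 10.7.2.2 and 10.8.2.2 already require upload of untreated S-ECG reports. This assumes that those reports show the request and the response, as the SAP ratio already needs for treated episodes. The SAP's syncope summary already covers both treated and untreated episodes. If adjudicated results are to be used, Section 21.2 or the CEC charter needs a line adding untreated episodes that contain an ATP request.

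The cost is a short SAP edit, a few more episodes to review and a possibly slightly lower reported rate. No site procedure or device programming changes.

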1.4 Pooling Analysis

1.5 Data Analysis for the DMC

Summaries of the AEs observed as part of the MODULAR ATP Clinical Study will be provided to the DMC in accordance to the timing outlined in the DMC Charter. These summaries will be performed by the MODULAR ATP statistician and he/she will attend the DMC meeting as requested by the DMC chair.
